9.1 Discontinuation

9.1.1 Discontinuation of study treatment

Discontinuation of study treatment for a patient occurs when study treatment is stopped earlier than the protocol planned duration, and can be initiated by either the patient or the investigator.

The investigator must discontinue study treatment for a given patient if he/she believes that continuation would negatively impact the patient's well-being.

Study treatment must be discontinued under the following circumstances:

- Patient/guardian decision
- Pregnancy
- Use of prohibited treatment as per recommendations in the prohibited treatment section
- Any situation in which study participation might result in a safety risk to the patient
- Following emergency unblinding
- Any severe suspected drug related AE at the investigator's discretion

- Suspected occurrence of angioedema. A patient with any signs or symptoms of clinically significant angioedema should be thoroughly evaluated by the investigator to determine if it constitutes a reason for discontinuation of study medication.
- Depending on the serum potassium, blood pressure, or eGFR, patient may need to have their study drug dose or the dose of another concomitant medication reduced or discontinued; or, if appropriate, have potentially contributing agents adjusted. Refer to appendices for treatment guidelines for hyperkalemia, hypotension or renal dysfunction, respectively.

If discontinuation of study treatment occurs, the investigator should make a reasonable effort to understand the primary reason for the patient's premature discontinuation of study treatment and record this information.

Patients who discontinue study treatment or who decide they do not wish to participate in the study further should NOT be considered withdrawn from the study UNLESS they withdraw their consent (see withdraw of informed consent section.). **Where possible, they should return for the assessments indicated** in the assessment schedule. If they fail to return for these assessments for unknown reasons, every effort (e.g. telephone, e-mail, letter) should be made to contact the patient/pre-designated contact as specified in the lost to follow-up section. This contact should preferably be done according to the study visit schedule.

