#### Date of first administration of study treatment

**Double-blind phase:** The date of first administration of study treatment in the double-blind phase is defined as the first date a dose of study treatment is administered and recorded on the First Dose of Study Treatment (Visit 2) electronic case report form (eCRF).

**Open-label phase:** The date of first administration of study treatment in the open-label phase is defined as the first date a dose of sacubitril/valsartan is administered in the open-label phase and recorded on the Study Treatment – Open Label eCRF.

The double-blind phase and open-label phase is only applicable for subjects enrolled under original protocol version 00.

With Protocol Versions 01, 02, 03 and 04 (Amendment 1, Amendment 2, Amendment 3, Amendment 4), all subjects will be in double-blind treatment throughout the study, and there is no open-label treatment phase.

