### Study phase

#### *Double-blind phase*

Participants recruited under Protocol Version 00 (Original Protocol) will receive either sacubitril/valsartan or valsartan during the first 8 weeks of the study. Assessments performed at Weeks 1, 2, 4, 6, 8 (including, but not limited to, vital signs) are assigned to the double-blind phase for summarization purposes. Unscheduled assessments are not assigned to a study phase for purposes of by-visit summaries.

Participants recruited under the amended protocols (verisons 01, 02, 03) and those participants recruited under Protocol Version 00 (Original Protocol) who opted to continue in an amendment protocol will receive either sacubitril/valsartan or valsartan during the approximately 84 weeks of the study. The assessments performed at Weeks 1, 2, 4, 6, 8, 10, 12, 16, 24, 32, 40, 48, 56, 68 or 84 (including, but not limited to, vital signs).

Participants recruited under the amended Protocol Version 04, assessments performed at Weeks 1, 4, 8, 24, 40, 56, 68 or 84 (including, but not limited to, vital signs) are assigned to the double-blind phase for summarization purposes. Unscheduled assessments are not assigned to a study phase for purposes of by-visit summaries.

For summarization of adverse events (AEs), notable vital signs and laboratory abnormalities, worsening renal function, defined as an increase in serum creatinine of  $\geq 0.5\text{mg/dL}$  and worsening of the eGFR by at least 25%, hyperkalemia (Potassium  $> 5.5\text{ mEq/l}$ ), angioedema and symptomatic hypotension by study phase, an assessment during the double-blind phase is defined as any assessment obtained in the following time interval:

- For participants recruited under the Protocol Version 00 (Original Protocol) date of first administration of study treatment through the date of the Week 8 visit, inclusive. For participants without a Week 8 visit, a projected Week 8 visit date will be derived relative to their treatment start date.

- For participants recruited under the amended protocols (versions 01, 02, 03 and 04) and participants recruited under Protocol Version 00 (Original Protocol) who opted to continue in the amended protocols date of first administration of study treatment through the date of the Week 84 visit, inclusive.

*Open-label phase (under the Protocol Version 00 (Original Protocol) )*

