For participants recruited under the Protocol Version 00 (Original Protocol) who do not continue in amendment protocol assessments performed at Weeks 10 or 12 (including, but not limited to, vital signs) are assigned to the open label phase for summarization purposes, unless otherwise noted. Unscheduled assessments are not assigned to a study phase for purposes of by-visit summaries.

For summarization of AEs, notable vital signs and laboratory abnormalities, and symptomatic hypotension by study phase, an assessment during the open label phase is defined as any assessment obtained in the following time interval:

After the date of the Week 8 visit. For participants without a Week 8 visit, a projected Week 8 visit date will be derived relative to their treatment start date.

Participants enrolled under Protocol Version 00 (Original Protocol) who died, withdrew consent, or were lost to follow-up prior to or on their projected Week 8 visit date will be excluded from the open-label phase.

End of Study (EOS)

EOS is obtained directly from the source data. A subject can discontinue treatment (EOT) at any time but continue the study, then the EOS is the study completion date. A subject who completes the study and has an EOS visit. If a subject discontinues the study for any reason, the discontinuation date is the EOS for that subject.

Follow-up for time-to-event analyses

For patients enrolled in the original protocol and continue to an open-label period, events are considered up to the end of their double-blind period (up to Week 8). For patients enrolled in Protocol Amendments 1-4, the events are considered up to their end of double-blind phase (EOS).

In-Hospital / Out-of-Hospital Randomization Status

The status for patient's in-hospital/out-of-hospital randomization is collected as "In-Patient or Out-Patient" category and will be provided by the Interactive Response Technology (IRT).

Year, month and week

For reporting purposes, the rules below will be followed to convert a year, month and week to days.

1 year = 365.25 days

1 month = 30.4375 days

1 week = 7 days

1 day = 24 hours

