## **2.3 Subject disposition, demographics and other baseline characteristics**

### **2.3.1 Subject disposition**

The number and percentage of subjects successfully screened will be presented. In addition, the reasons for screen failures will be provided. For subjects who are screened more than once, the information from the last screen will be used in the summary. This analysis will be performed on All subjects.

Number of subjects who were randomized will be presented on screen passed subjects.  
The following categories will be summarized on RAN:

- Number and percentage of subjects who were treated
- Number and percentage of subjects who prematurely discontinued study treatment during double-blind phase
- Number and percentage of subjects who prematurely discontinued study treatment during double-blind phase, excluding deaths
- Number and percentage of subjects who prematurely discontinued study treatment during open-label phase
- Number and percentage of subjects who prematurely discontinued study treatment during open-label phase, excluding deaths
- Reasons for premature discontinuation of study treatment (separately for double-blind phase and open-label phase)
  - Adverse Event
  - Death
  - Lost of Follow-Up
  - Study terminated by sponsor
  - Patient/Guardian decision
  - Protocol deviation
  - Physician decision
  - Pregnancy

Study duration in months [(date of last contact/death – date of first dose of study treatment + 1)/30.4375]

The following categories will be summarized by treatment group for the full study period (Baseline – Week 84 end)

- Subjects who received at least 1 dose of study treatment in the study period
- Subjects who did not receive at least 1 dose of study treatment in the study period and the reason

Furthermore, it will only be feasible to determine loss to follow-up at Week 84 end.

Subject disposition (total enrolled, total discontinued, total completed) by region (US and Canada) and pandemic phase will also be summarized for the RAN.

A summary of subjects who were randomized but did not meet the inclusion criteria #3, i.e. subjects enrolled outside of the respective protocol window will be provided. The summary will include subjects randomized with/without the protocol specified enrollment window (i.e., Original protocol 36H-10Days; Amendment 1-3 36H-30Days; Amendment 4 0H-30Days) by original protocol and amendments by treatment for RAN.

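### For Version 00 patients, the open-label safety phase starts by visit date and requires no open-label dose, so unexposed patients and pre-dose days are labelled open-label

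*SAP*

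**What the plan says.** Version 00 had 8 weeks of double-blind treatment followed by 4 weeks of open-label sacubitril/valsartan (SAP 1.1). For patients who did not continue into an amendment, SAP 2.1.1 (Study phase) places safety events as follows.

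- Double-blind: from the "date of first administration of study treatment through the date of the Week 8 visit, inclusive".
- Open-label: "After the date of the Week 8 visit". If there was none, a calendar date is used: "For participants without a Week 8 visit, a projected Week 8 visit date will be derived relative to their treatment start date".
- Exclusions from open-label: only patients who "died, withdrew consent, or were lost to follow-up prior to or on their projected Week 8 visit date will be excluded".

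The same section defines the start of open-label dosing as the "first date a dose of sacubitril/valsartan is administered in the open-label phase and recorded on the Study Treatment" open-label eCRF page. Neither phase interval refers to that date.

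The SAP's End of Study definition lets a subject stop treatment and remain in the study. Protocol 9.1.1 agrees: "Patients who discontinue study treatment or who decide they do not wish to participate in the study further should NOT be considered withdrawn" unless they withdraw consent.

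The phases are used for treatment-emergent AEs (SAP 2.7.1.3), exposure-adjusted rates by phase and treatment group (2.7.1.6) and deaths (2.7.2). SAP 2.3.1 also lists, among its summaries on the randomized set: "Number and percentage of subjects who prematurely discontinued study treatment during open-label phase".

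**The concern.** A phase named for a drug should contain time on that drug. Here the boundary is a clinic date, and the only conditions for entry are being alive, consenting and still in contact. Two mislabellings follow from the text alone. Patients who never took open-label sacubitril/valsartan are counted in its phase, and days before its first dose are counted as belonging to it. A third depends on when the first open-label dose is taken. If it is taken on the Week 8 visit date, a reaction to it that day is tabulated as a double-blind event. For a patient randomized to valsartan, that event goes to the comparator.

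At stake are the by-phase incidence tables and exposure-adjusted rates, and the reading of events that tend to follow a first dose closely, such as symptomatic hypotension.

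**Working it through.** The plan states no figure for this point. Its one design calculation (450 patients, 85% power, SAP 3) does not use study phases. The check is therefore a reading of the rules, followed by illustrations under stated assumptions.

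**1. Apply the rules to four Version 00 patients.**

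| Patient | Open-label exposure at the event | SAP phase |
|---|---|---|
| A. Stops drug at Week 3, stays in follow-up, AE at Week 10 | None, ever | Open-label |
| B. AE after the Week 8 visit date but before the first open-label dose | None yet | Open-label |
| C. First open-label dose on the Week 8 visit date, reaction that day | Yes | Double-blind, randomized arm |
| D. AE on the Week 8 visit date, first open-label dose the next day | None yet | Double-blind |

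D is labelled correctly. A is wrong whatever the dosing day. B is wrong whenever there is a gap. C is wrong only if dosing starts at the visit.

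**2. Does another rule repair this?** The safety set needs one dose of any study treatment (SAP 2.2), so A stays in. The on-treatment period runs to the last study visit (SAP 2.7), so A's off-drug event stays in too. The time-to-event rule in SAP 2.1.1 does refer to patients who go on to an open-label period, but the safety phase rule has no such condition.

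**3. Effect of unexposed patients on crude incidence.** Let q be the share of the phase never exposed, p_e the risk in exposed patients and p_u the risk in the unexposed. The table shows (1 − q)·p_e + q·p_u. The documents give none of these. Assume p_e = 10% and p_u = 0:

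- q = 5%: 0.95 × 10% = 9.5%
- q = 10%: 0.90 × 10% = 9.0%
- q = 20%: 0.80 × 10% = 8.0%
- q = 30%: 0.70 × 10% = 7.0%

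The direction is not fixed. With q = 20% and p_u = 20%, the result is 8% + 4% = 12%. In the exposure-adjusted rates, an unexposed patient's event can enter the numerator while adding little or no open-label exposure time.

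**4. Effect of one same-day event (case C only).** One event adds 1/n to the valsartan double-blind incidence. If Version 00 has 10, 25 or 50 valsartan patients, that is 10, 4 or 2 percentage points. Pooled over 450/2 = 225, it is 1/225 = 0.4 points.

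**5. Expected number of such events.** Assume 20 to 80 patients entered open label, half of them from valsartan, with a 0.5% to 2% first-day risk. The lower end is 10 × 0.5% = 0.05 and the upper end is 40 × 2% = 0.8, so fewer than one event is expected.

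**The case against.** The case on the other side is substantial.

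- **Same-day dosing is not documented.** A reader might infer that reactions to open-label sacubitril/valsartan will be charged to valsartan. The Version 00 protocol is not supplied, and neither document says on which day open-label drug starts. If it starts the day after the visit, the inclusive cut is right. This part holds only as a conditional.
- **The visit-date cut suits visit data.** Laboratory values and vital signs from the Week 8 visit belong to the double-blind phase. This stands, and it rules out a simple rule that sends everything on the first-dose date to open-label, because an AE found from that visit's blood draw would then be mislabelled in the other direction.
- **Angioedema would not be hidden.** SAP 2.7.4.6 tabulates it separately for open-label sacubitril/valsartan, with timing relative to dosing. This stands.
- **The open-label list is narrower.** It names AEs, notable vital signs and laboratory abnormalities, and symptomatic hypotension. Hyperkalemia, worsening renal function and angioedema are named only in the double-blind list. This stands for those definitions, although such an event reported as an AE still follows the AE rule.
- **The 450 denominator is not established.** A reader might infer that open-label discontinuations are divided by all 450 randomized patients, so that a true 10% in 20 to 80 patients shows as 2/450 = 0.4% to 8/450 = 1.8%. SAP 2.1.1 says the open-label phase applies only to Version 00 patients, and 2.3.1 names the analysis set without stating that denominator. Only a clarification is needed.
- **Counting events after drug is stopped is the SAP's general convention.** That is acceptable under the randomized arm. It does not justify moving those events into a phase whose drug the patient never took.
- **Few patients may be affected.** Protocol 6.4.1 asks for an end of study visit when drug is stopped completely, and the Protocol 9.1.1 text is that of the current amendment. However, the open-label exclusions do not include stopping drug, and the SAP's own End of Study wording allows such patients to continue.

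**Conclusion.** The point holds as a defect in a safety definition. Without further assumption, the SAP admits patients to the open-label phase who had no open-label dose, and it counts any gap before the first dose as open-label. Charging a first-dose reaction to the randomized arm is possible only if dosing starts on the Week 8 visit date, which the documents leave open.

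The size cannot be determined, because neither the number of Version 00 patients nor the share unexposed is stated. The percentages above are illustrations. Their practical message is that dilution could be a few points in a small phase population and that misassigned same-day events would probably number fewer than one.

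The effect stays within the by-phase safety summaries, for Version 00 patients who did not continue into an amendment. A reader might infer that efficacy is touched, but the primary NT-proBNP analysis does not use this rule. The correction is worth making because the plan already collects the date it needs.

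**What to change.** In SAP 2.1.1, for Version 00 patients who did not continue into an amendment:

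1. Limit the open-label phase to patients with at least one dose on the open-label study treatment eCRF, and start it at that first dose date.
2. List post-Week 8 events of patients with no open-label dose separately.
3. For events on the first open-label dose date, use recorded timing relative to the dose where it exists. Keep findings and AEs that come from the Week 8 visit laboratory tests, vital signs or examination in the double-blind phase. Flag the remaining same-day events of unknown timing and show them under both assignments.

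In SAP 2.3.1, state that open-label discontinuation percentages use patients who received open-label drug as the denominator.

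The cost is SAP wording and reprogramming of the phase flag before database lock. The dose date is already collected. Sample size, power and the primary analysis do not change.

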## COVID-19 pandemic phases

The participants in this trial may be divided into 3 subsets based on the COVID-19 pandemic status:

- Before pandemic set: Participants who completed (or discontinued) the trial (or completed study treatment period) before the pandemic start date
- During pandemic set: Participants with at least one on-treatment assessment or treatment-emergent event during the pandemic date
- After pandemic set: Participants who were enrolled (based on informed consent date) in the study after the pandemic end date (if applicable)

Where 01-Mar-2020 is the defined start date for the COVID-19 pandemic in the US and Canada according to the [COVID-19 Guidance Dates by region for sensitivity analyses V5.0 \(novartis.net\)](https://novartis.net).

## 2.2 Analysis sets

The following analysis sets will be used for the statistical reporting and analyses:

Randomized Analysis Set (RAN)	The RAN will consist of all randomized subjects.
The Full Analysis Set (FAS)	The FAS will consist of all subjects to whom study treatment has been assigned by randomization and at least one dose of study treatment received. According to the intent-to-treat principle, participants will be included for analysis according to the treatment they have been assigned to during the randomization procedure.
The Safety Set (SAF)	The SAF includes all participants who received at least one dose of the study treatment. Participants will be included for analysis according to the study treatment they received, where treatment received is defined as the randomized treatment if the participant took at least one dose of that treatment or the first study treatment received if the randomized treatment was never received.

The subjects in this trial are divided in 2 groups, (1) those who are randomized under Protocol Version 00 (Original Protocol subjects) and (2) those who are randomized after site execution of the amended protocols (Amendment 01, 02, 03, and 04 subjects). The FAS includes subjects from both groups.

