12.1 Analysis sets

The Randomized Analysis Set (RAN) consists of all randomized participants.

The Full Analysis Set (FAS) comprises all participants to whom study treatment has been assigned by randomization. According to the intent-to-treat principle, participants will be included for analysis according to the treatment they have been assigned to during the randomization procedure.

The Safety Set (SAF) includes all participants who received at least one dose of study treatment. Participants will be included for analysis according to the study treatment they received, where treatment received is defined as the randomized treatment if the participant took at least one dose of that treatment or the first study treatment received if the randomized treatment was never received.

The patients in this trial are divided in two groups, (1) Those who are randomized under Protocol Version 00 (Original Protocol patients) and (2) Those who are randomized after site execution of Protocol Version 01 (Amendment 1 and subsequent amendment patients). FAS includes patients from both groups. See [Section 3](#) for details.

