## **2.6 Analysis of secondary objectives**

All analyses will be performed on the FAS, unless otherwise specified.

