### **2.6.1 Secondary endpoints**

Secondary endpoints include the following:

1. The composite hierarchical outcome consisting of a) time to CV death, b) number and times of HF hospitalizations during follow-up, c) number and times of urgent HF visits during follow-up, and d) time-averaged proportional change in NT-proBNP (from Baseline to Weeks 4 and 8)

2. The cumulative number of recurrent composite events overtime, ie, the total number of composite events of HF hospitalizations, urgent HF visits, and CV death.
3. Incidences of a composite endpoint of worsening renal function defined as:
  - renal death
  - reaching end-stage renal disease (ESRD)
  - $\geq 50\%$  decline in estimated glomerular filtration rate (eGFR) relative to baseline
4. Proportional change in NT-proBNP from Baseline to Week 8
5. Proportional change in hs-Troponin (high sensitivity) from Baseline to Weeks 4 and 8
6. Dosing levels and discontinuations
7. Incidence of adverse events of special interest during treatment
  - Incidence of symptomatic hypotension
  - Incidence of hyperkalemia (potassium  $> 5.5$  mEq/L)
  - Incidence of angioedema
  - Incidence of worsening renal function, defined as an increase in serum creatinine of  $\geq 0.5$  mg/dl and worsening of the eGFR by at least 25% (based on central laboratory data).

All these secondary endpoints will be analyzed using FAS and nominal p-values will be reported. There will be no adjustment for multiplicity.

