### **2.6.2.1.1 Handling of missing values/censoring/discontinuations**

For the calculation of the win-ratio an initial time “at risk” (follow-up) for each subject will be calculated as number of days from treatment start date to their attained:

- Date of last visit (End of Study visit)
- Date of death from any cause
- Date of withdrawal of informed consent
- Date of loss to follow up

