#### **2.6.2.1.2 Sensitivity Analysis:**

Three sensitivity analyses are planned for secondary endpoint 1.

- The primary analysis of the win ratio will be repeated but will also include HF hospitalizations that are adjudicated as Possible HF Hospitalization (i.e. are insufficient data to meet PARAGLIDE-HF criteria) in addition to confirmed HF hospitalizations.
- The primary analysis of the win ratio will be repeated but data for CV death, HF hospitalizations and urgent HF visits will be based on investigator reporting and not adjudicated data.
- The primary analysis of the win ratio will be repeated but data that occurs after diagnosis as COVID-19 positive will be censored at the subject level.

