**2.6.2.2.1 Sensitivity Analysis:**

Four sensitivity analyses are planned for secondary endpoint 2.

- The primary analysis of the LWYY model will be repeated but will also include HF hospitalizations that are adjudicated as Possible HF Hospitalization (i.e. are insufficient data to meet PARAGLIDE-HF criteria) in addition to confirmed HF hospitalizations meeting PARAGLIDE-HF criteria
- The primary analysis of the LWYY model will be repeated but data for CV death, HF hospitalizations and urgent HF visits will be based on investigator reporting and not adjudicated data.
- The primary analysis of the Secondary endpoint 2 will be repeated with Kaplan-Meier estimates for time to the first composite event by the treatment group, in tables and graphs.
- The primary analysis of the LWYY model will be repeated but data that occurs after diagnosis with COVID-19 positive will be censored at the subject level.

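### The SAP limits the full analysis set to dosed patients where the protocol includes everyone randomised, and starts the win-ratio clock at treatment start instead of randomisation

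*SAP*

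**What the plan says.** **Analysis set.** Protocol 12.1 states: "The Full Analysis Set (FAS) comprises all participants to whom study treatment has been assigned by randomization". The synopsis agrees, and neither text sets a dosing condition. SAP 2.2 uses the same name and the same intent-to-treat label, but requires treatment to be "assigned by randomization and at least one dose of study treatment received". SAP 2.5.1 and 2.5.2 use this FAS for the primary endpoint. For the secondary objectives, SAP 2.6 says "All analyses will be performed on the FAS, unless otherwise specified" and SAP 2.6.1 says "All these secondary endpoints will be analyzed using FAS and nominal p-values will be reported".

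**Undosed patients.** SAP 2.3.1 will report, by arm, "Subjects who did not receive at least 1 dose of study treatment in the study period and the reason". Protocol 8.1.1 classes patients who are randomised but never start treatment as early terminators.

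**Time origin.** In SAP 2.6.2.1.1, win-ratio time at risk "will be calculated as number of days from treatment start date to their attained" end date. Protocol 12.5.1 times CV death from randomisation, and so does the recurrent-event (LWYY) model in SAP 5.4.3.

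**LVEF factor.** Protocol 12.4.1 and the synopsis split baseline LVEF at 57% in the primary ANCOVA. SAP 2.5.2 and 5.4.1 split it at the median.

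**The concern.** The two governing documents give one name to two different groups of patients, and the SAP's group is selected on something that happens after randomisation. Under the SAP definition the FAS and the safety set contain the same people and differ only in the arm to which a patient is counted. That is hard to square with the intent-to-treat label. It also sits badly with the SAP's own Estimand 1, whose population comes from the eligibility criteria and whose strategy for treatment discontinuation is treatment policy.

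The time origin is tied to this. A patient who never took a dose has no treatment start date, so restoring the protocol's FAS without changing the clock would leave that patient's win-ratio follow-up undefined. The study-day rule in SAP 2.1.1 has the same gap. At stake is whether the primary and secondary comparisons are those that randomisation supports, and whether the choice of set is settled before unblinding.

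**Working it through.** **1. Is there an all-randomised efficacy analysis elsewhere?**
- The SAP's all-randomised set is used for disposition (2.3.1) and for the qualifying event (2.3.3), not for efficacy.
- Sensitivity analysis 4 of the primary endpoint (SAP 2.5.7) opens by referring to every randomised subject. It then splits them by enrolment window, builds the within-window group from the FAS, and uses FAS data.
- For the win ratio, "Three sensitivity analyses are planned for secondary endpoint 1"; for the LWYY model, "Four sensitivity analyses are planned for secondary endpoint 2". These vary the adjudication, the COVID-19 censoring or the event definition. None adds undosed patients.
- Appendix B pools all enrolled or randomised patients of this trial with patients from other trials, and is expressly outside the CSR.
- Section 2.12, which Appendix B cites for outcome models, is not in the supplied copy, and only the all-randomised row of Table 5-3 is legible.

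So none is visible for this trial alone in the CSR analyses supplied.

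**2. Reproducing the stated power.** Inputs (SAP 3): 450 patients, ratio 0.77, SD 0.85, two-sided 0.05, 15% missing.
- Evaluable per arm: 450 × 0.85 / 2 = 191.25
- Difference: |ln 0.77| = 0.2614
- Standard error: 0.85 × √(2/191.25) = 0.0869
- Power: Φ(0.2614/0.0869 − 1.96) = 0.852, against 85% stated

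The stated power therefore rests on all 450 randomised patients less 15%.

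**3. Effect of the dosed set on primary power.** The number undosed is not in the documents; 1% to 3% (4.5 to 13.5 of 450) is my assumption. If that loss comes on top of the 15%, power is 0.849 at 1%, 0.845 at 2% and 0.842 at 3%. If undosed patients are already inside the 15%, power does not change.

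**4. Effect on the win ratio.** All pairs: 225 × 225 = 50,625. With the undosed split evenly between arms:
- 1% undosed removes 1 − 0.99² = 1.99% of pairs (1,007)
- 3% undosed removes 1 − 0.97² = 5.91% of pairs (2,992)

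Most of these pairs would be ties. Suppose undosed patients leave by Week 8 without NT-proBNP values. Assume 26.7 events per 100 patient-years in both arms, the valsartan rate that protocol 1.1 gives for patients hospitalised within 30 days, with Poisson events.
- Events per patient in 8 weeks: 0.267 × 56/365.25 = 0.0409
- Share of such pairs decided: 1 − exp(−2 × 0.0409) = 7.9%
- Wins or losses forgone: 1.99% × 7.9% = 0.16% and 5.91% × 7.9% = 0.46% of all pairs

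If they leave at once, this is near zero.

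**5. Effect on event counts and the rate ratio.**
- Over 8 weeks: 4.5 × 0.0409 = 0.18 to 13.5 × 0.0409 = 0.55 events
- Over the 46-week average duration (0.882 years, an upper bound): 4.5 × 0.235 = 1.1 to 13.5 × 0.235 = 3.2 events

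Person-time is removed along with the events. Taking all 13.5 patients from one arm at the common rate, that arm goes from 52.96/198.36 = 0.267 to (52.96 − 3.18)/(198.36 − 11.90) = 0.267. The rate ratio moves only if undosed patients have a different event rate and are unevenly split between arms.

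**6. Clock for dosed patients.** SAP 2.1.1 takes the first dose from the Visit 2 form, and Visit 2 is the randomisation visit. The shift should therefore be short for anyone who was dosed.

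**The case against.** The strongest reply is that little can go wrong in practice. The trial is double-blind and double-dummy from randomisation (protocol 6.1 and 6.3), so whether a first dose is taken should not depend on knowledge of the arm. Undosed patients are early terminators, and most would lack both Week 4 and Week 8 values; protocol 12.4.2 leaves such patients out of the primary analysis anyway. Their number and reasons will be reported, and the secondary p-values are nominal. Inside the SAP's own set every patient has a treatment start date, so the missing-date problem appears only once the FAS is widened. Protocol section 12 also leaves analysis details to a SAP finalised before lock. All of this stands as an argument about size. It does not settle which patients are to be analysed, since the protocol has already chosen, and reporting the undosed does not return them to the comparison.

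A reader might infer three stronger things that the documents do not support:
- **That no all-randomised efficacy analysis is planned at all.** Sensitivity analysis 4 is ambiguously worded, Appendix B does pool all patients, and section 2.12 and the FAS row of Table 5-3 cannot be checked.
- **That the results will be biased or underpowered.** The calculations show no such effect at the assumed rates.
- **That the changes were made without declaring them.** SAP section 4, where they would be recorded, shows no text in the supplied copy.

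**Conclusion.** The mismatch in the analysis set is real and is in the current text of both documents, as is the mismatch in the win-ratio time origin. Both should be corrected before database lock. The case rests on keeping the randomised comparison and on having one definition, not on power or a demonstrated bias. The practical effect is probably small. It cannot be sized without the number undosed, and every figure above depends on the assumed 1% to 3%; the pair and event figures also depend on the borrowed event rate.

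The LVEF cut is a minor reconciliation item. The split ignores treatment and should barely move the estimate. A median does, however, change with the analysis set, and the SAP does not say in which population it is taken; 57% is fixed. The race factor is listed only in the protocol synopsis. Protocol 12.4.1 and the SAP both omit it, so that is an inconsistency within the protocol and not a SAP error.

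**What to change.** - **SAP 2.2:** delete the dosing condition, so that the FAS is all randomised patients, as in the protocol, for the primary endpoint and secondary endpoints 1 to 5. Keep the dosed set, by assigned arm, as a sensitivity analysis.
- **SAP 2.6.2.1.1:** start time at risk at randomisation.
- **SAP 2.1.1:** for untreated patients count study day from randomisation, in line with the baseline rule already given there for them.
- **Endpoints 6 and 7 (dosing, discontinuations, events during treatment):** protocol 12.5.1 names the FAS for these too. Either use it with the dosed set alongside, or keep the dosed set and record this in SAP section 4 as a departure from the protocol.
- **SAP 2.5.7:** say plainly which set sensitivity analysis 4 uses.
- **SAP 2.5.2 and 5.4.1:** use the 57% cut, unless SAP section 4 already records the change to the median. Note there that 12.4.1, not the synopsis, is followed on race.

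The cost is SAP wording, one population flag and one start date. Bringing the SAP back to the protocol needs no protocol amendment; editing the synopsis text on race would. The downside is slight dilution. If undosed patients had complete data and no treatment effect, the difference would shrink to 0.2614 × (1 − u), where u is the undosed share. Power would then be 0.845 at 1% and 0.838 at 2%, against 0.852. Since most would have no Week 4 or 8 value, the real loss should be smaller.
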